9.4. REASONS FOR DISCONTINUATION	24
9.5. LENS INFORMATION.....	24
9.6. LENS FITTING CHARACTERISTICS	25
10. CHANGES IN THE PLANNED ANALYSIS.....	25
11. REFERENCES.....	26
12. APPENDICES	29
12.1. SCHEDULE OF STUDY PROCEDURES.....	29
12.2. MISSING DATA PATTERN.....	31
12.3. SAS CODE FOR SENSITIVITY ANALYSIS	32

List of Abbreviations

AE	Adverse Event/Adverse Experience
CFR	Code of Federal Regulations
CLUE	Contact Lens User Experience
CLPU	Contact Lens induced Peripheral Ulcer
CS	Compound Symmetry
██████████	██████████
D	Diopter
eCRF	Electronic Case Report Form
ETDRS	Early Treatment Diabetic Retinopathy Study
FCS	Fully Conditional Specification
GCP	Good Clinical Practice
HIPAA	Health Insurance Portability and Accountability Act
IB	Investigator's Brochure
ICH	International Conference on Harmonization
IOP	Intraocular Pressure
IRT	Item Response Theory
ISO	International Organization for Standardization
J&J	Johnson & Johnson
logMAR	Logarithm of Minimal Angle of Resolution
MI	Multiple Imputation
mITT	Modified Intention-to-Treat
OD	Right Eye
OS	Left Eye
PRO	Patient Reported Outcome
SAS	Statistical Analysis System
SEALS	Superior Epithelial Arcuate Lesions
SIE	Significant Infiltrate Event
SLF	Slit Lamp Findings
SD	Standard Deviation
VA	Visual Acuity
UN	Unstructured

1. Introduction

This statistical analysis plan (SAP) describes the analyses and data presentations for protocol CR-5930 v3.0 Amendment 2.0 dated 31 October 2017. This study is a multi-site, double-masked, randomized controlled trial.

This document will serve as the final guidance for all the statistical analysis for this study and will supersede the Statistical Method section (section 14) in the protocol if there are any discrepancies.

The etafilcon A with ketotifen contact lens is being developed as a novel drug/device combination product that incorporates the anti-allergy agent ketotifen with the same material as the 1•DAY ACUVUE® Brand disposable contact lens (etafilcon A daily disposable contact lens). This new product will be referred to hereafter as K-Lens. The control 1•DAY ACUVUE® Brand disposable contact lens will be referred to hereafter as Placebo. Ocular allergy, and the discomfort associated with its signs and symptoms, is a common cause of contact lens intolerance and of seasonal exacerbation of eye allergy symptoms in contact lens wearers. The creation of a concomitant system of an anti-allergy agent and a contact lens will offer significant advantages over existing therapies in that it allows contact lens users to continue wearing their lenses during the allergy season while preventing ocular itching associated with allergic conjunctivitis.

K-Lens has been evaluated for safety, tolerability, and efficacy (prevention of ocular itching) in previous studies⁹⁻²⁰. The results of these studies have shown it to be safe, tolerable and efficacious. Two (2) pivotal Phase 3 studies have shown that K-Lens was effective in the prevention of ocular itching associated with allergic conjunctivitis at 15 minutes and 12 hours following lens insertion^{16, 17}. The goal of this study is to evaluate the clinical performance of K-Lens produced on the new J&J Vision Care, Inc. manufacturing line in Limerick, Ireland, in a population of normal, healthy, habitual contact lens wearers.

Additionally, in the previous K-Lens studies, visual acuity was assessed using Snellen visual acuity charts which are commonly used in clinical practice. The proposed clinical study will assess visual acuity using logMAR (ETDRS) charts which are more commonly used in clinical research studies. By collecting data from both types of visual acuity charts, a more comprehensive assessment of visual acuity with K-Lens will be obtained.

For additional clinical information regarding K-Lens, refer to the latest version of the Investigator's Brochure.²¹

2. Objectives

The purpose of this study is to evaluate the clinical performance of K-Lens produced on the new J&J Vision Care, Inc. manufacturing line in Limerick, Ireland.

3. Investigational Plan

3.1. Overall Study Design and Plan

This is a randomized, double-masked, bilateral, controlled, two-arm parallel group, multi-site, 1-week dispensing study. Approximately 132 subjects will be screened and randomly assigned to either K-Lens or Placebo using 2:1 ratio (i.e. 2/3 of subjects on the K-Lens arm and 1/3 on the Placebo arm). The goal is for a sample size of 120 (80 subjects in K-lens and 40 subjects in Placebo) after subjects who withdraw or are lost-to-follow-up.

The study begins with an Initial Visit (Visit 1). If a subject is found to meet all eligibility criteria, they will be randomized and fit with either the K-Lens or Placebo lens in both eyes based on the randomization scheme provided to the investigators; otherwise, the subject will be deemed ineligible for this study.

Successfully dispensed subjects at the initial visit will be scheduled for a follow-up visit (Visit 2). The follow-up visit will occur approximately 6 to 9 days after the Initial Visit. Unscheduled follow-up visits may occur during the study. Subjects will be advised to wear the study lenses at least 8 hours a day for a minimum of 6 days.

Both study lenses will be worn as a daily disposable modality. J&J Vision Care (JJVC) will provide the investigational sites with sufficient quantities of study lenses and supplies to complete the study.

The Investigator is responsible for ensuring that all subjects entering the study conform to subject selection criteria. The number of subjects targeted for randomization and completion are as follows:

Table 1: Target number of subjects by arm and site

	K-Lens	Placebo	Total
Randomization	88	44	132
Completion	80	40	120
Number of sites	6	6	6
Subjects/site (Min-Max)	12-16	5-9	20-24

The schedule of events is reported in section 12.1.

3.2. Study Endpoints

3.2.1. Primary Endpoint

The primary endpoint is monocular contact lens-corrected distance visual acuity using a logMAR visual acuity scale. This will be evaluated under high luminance and high contrast conditions at 4 meters from ETDRS charts at the 1-week follow-up visit for each eye. The analysis will be conducted at subject level, so each eye evaluation will be considered as a repeated measure for the same subject.

The subject is asked to read the visual acuity chart and the investigator will report in eCRF the letters missed by the subject and the logMAR score will be derived in eCRF. In case the subject is unable to read at least 3 letters on the top line of the chart, the investigator will repeat the assessment at a closer distance: The subject starts at 4 meters, then will be moved to 3 meters then 0.5m closer at a time (e.g. 4m, 3m, 2.5m, 2.0m). If the subject correctly reads all 5 letters on the last line, the test will be stopped and 0 missing will be recorded without moving subjects further away from the chart.

The procedure is explained in the [REDACTED] in Appendix D of the study protocol.

3.2.2. Secondary Endpoints

FDA Biomicroscopy Scale

This secondary endpoint is a binary response measured at eye level over the post-fit period including unscheduled visits between Visit 1 and Visit 2:

- Yes = eye has at least one clinically significant (Grade 3 or Grade 4) slit lamp finding;
- No = otherwise.

An eye with multiple clinically significant slit lamp finding events will be counted only once.

The FDA Biomicroscopy Scale measures the severity of the ocular clinical findings and goes from Grade 0 (none) to Grade 4 (severe). The procedure is explained in the [REDACTED] in Appendix D of the study protocol. The individual ocular finding results are considered as other endpoints, these are described in section 3.2.3 Slit-lamp findings.

Unacceptable Lens Fitting

This secondary endpoint is a binary response (yes/no) measured at eye level at fitting and post-fitting evaluations including unscheduled visits:

- Unacceptable = unacceptable fit due to meeting one of the following criteria:
 - limbal exposure at primary gaze or with extreme eye movement;
 - edge lift;
 - excessive movement in primary up gaze;

- insufficient movement in all three of the following conditions: primary gaze, up gaze, and push up test.
- Acceptable = otherwise.

This will be recorded on the eCRF as whether the fit is unacceptable or not.

Subjects discontinued because of unacceptable fitting will also be counted as having an Unacceptable response. An eye with multiple unacceptable fitting events will be counted only once.

The procedure is explained in the [REDACTED] in Appendix D of the study protocol. The individual lens fitting characteristics are considered as other endpoints, these are described in section 3.2.3 Lens Fitting Characteristics.

3.2.3. Other Endpoints

Average daily wear time (in Hours):

Average daily wear time will be calculated as the number of hours between subjects reported time of insertion and time of removal of the study lenses, on an average day, at 1-Week Follow-up evaluation.

Subjective assessment of lens handling:

Lens handling will be assessed using Contact Lens User Experience™ (CLUE) questionnaire at 1-Week Follow-up evaluation. CLUE™ is a validated patient reported outcomes (PRO) questionnaire to assess patient-experience attributes of soft contact lenses (comfort, vision, handling, and packaging) in a contact-lens wearing population in the US, ages 18-65. Derived CLUE™ scores using Item Response Theory (IRT) follow a normal distribution with a population average score of 60 (SD 20), where higher scores indicate a more favorable/positive response with a range of 0-120. A 5-point increase in an average CLUE™ score translates into 10% shift in the distribution of scores for population of soft contact lens wearers.²² The handling scores will be generated using the flexMIRT software version 3 or higher (Chapel Hill, NC).

Slit-lamp findings:

Frequency and severity by eye of slit lamp findings (SLFs) including conjunctival injection, corneal edema, corneal neovascularization, corneal staining, tarsal abnormalities or any other complications. SLFs will be evaluated at fitting and post-fitting evaluation visits including unscheduled visits.

Subject's Reported Ocular Symptoms:

Frequency and severity by eye of subject's reported ocular symptoms and problems with the study lens at fitting and post-fitting evaluation visits including unscheduled visits.

Severity of the symptoms can be:

- 0 = Not Applicable or Not Recorded;
- 1 = Mild and results in little or no interference with lens wear;
- 2 = Moderate AND/OR occasionally interferes with lens wear;
- 3 = Severe AND/OR frequently interferes with lens wear.

The related procedure is explained in [REDACTED] in Appendix D of the study protocol.

Lens fitting characteristics:

Frequency by eye of mechanical lens fitting characteristics at fitting and 1-Week Follow-up evaluations. Lens fitting characteristics to be reported are:

- Lens Centration Grade
- Decentered Direction
- Limbal Exposure Grade
- Edge Lift (Present or Absent)
- Primary Gaze Movement Grade
- Upgaze Movement Grade
- Lens Tightness Grade (Push-up Test)
- Acceptable Fitting (yes/no)

Additional Endpoints

- Adverse events
- Discontinuation
- Reason for discontinuation
- Unscheduled lens replacement
- Reasons for unscheduled lens replacement including lens damage.

4. General Statistical Considerations

Continuous data will be summarized descriptively by n, mean, standard deviation (SD), median, minimum (Min) and maximum (Max). Minimum and maximum will be presented to the same number of decimal places as the raw data, mean and median will be presented to 1 more decimal place than the raw data, and standard deviation will be presented to 2 more decimal places than the raw data.

Categorical data will be summarized descriptively by frequency: n (%). The denominator for all percentages will be the number of subjects (or eyes as applicable) available, once pooled, within that treatment group for the analysis set of interest, unless otherwise indicated. Percentages will be presented to 1 decimal place and will not be displayed for zero frequencies. A row denoted “Missing” will be included in count tabulations where necessary to account for missing values.

All data summaries and statistical analyses will be performed using the SAS software version 9.3 or higher (SAS Institute, Cary, NC).

All planned analysis will be conducted with an overall type I error rate of 5%. Unless otherwise specified, all statistical tests will be 2-sided.

P-values will be rounded to 3 decimal places. P-values that round to 0.000 will be presented as '<0.001' and p-values that round to 1.000 will be presented as '>0.999'.

Study day of an event that occurred after or on the first Fitting date will be calculated as Event Date – First Fitting Date + 1.

Study day of an event that occurred before the first dose date will be calculated as Event Date – First Fitting Date.

Baseline is last assessment obtained prior to the insertion of the test or control lenses, unless otherwise specified. Some subjects may have up to four baseline evaluations if a damaged lens needs to be replaced and/or due to failure to fulfil inclusion criteria and/or due to fulfilment of exclusion criteria. In this case, the last baseline evaluation will be considered in the descriptive summary and analysis. For subjects enrolled but not randomized the last non-missing assessment will be taken as baseline.

Some subjects may have up to two Visit 1 evaluations, if a damaged lens needs to be replaced and/or due to failure to fulfil inclusion criteria and/or due to fulfilment of exclusion criteria. In this instance, the last Visit 1 evaluation will be considered in the descriptive summary and analysis.

Missing or spurious values will not be imputed as the number of missing values is expected to be low. The count of missing values will be included in the summary tables and listings.

Subject dropout is expected to be one of the main reasons for missing data in this clinical trial. Past clinical trials don't provide the evidence that subject dropout is systematic or not-at-random. To evaluate the impact of missing data, a sensitivity analysis will be conducted using multiple imputation methods.

All listings will be sorted for presentation in order of study center and subject. Key variables to be displayed on each listing will be: Center, subject id, age, sex and race.

4.1. Sample Size

Assuming a perfect correlation between left eye visual acuity and the right eye visual acuity (worst case scenario), the total sample size (n) required to achieve 85% power with two-

sided type I error of 0.05 was calculated for different scenarios of mean difference (Δ = K-Lens – Placebo) and common standard deviation (σ) in the two arms. The results are summarized in the Table below:

Table 2: Sample size for different scenarios of mean Δ and σ

Δ	σ	n
0	0.05	15
0	0.01	45
0.04	0.05	33
0.04	0.1	117

The sample size calculation was conducted using the PROC POWER Procedure (SAS/STAT 14.1, SAS Institute, 2015) for two-sample means with allocation weight of 2:1.

The sample size of 120 subjects is considered sufficiently large to test for non-inferiority with a minimum statistical power of 85% and two-sided type I error of 0.05.

The plan is to enroll 132 eligible subjects with a target completion of 120 subjects (80 subjects in K-Lens and 40 subjects in Placebo).

4.2. Randomization, Stratification, and Blinding

Subjects will be randomly assigned to either K-Lens or Placebo arm based on a computer-generated randomization schedule prepared before the start of the study. The randomization will be stratified by investigational site and randomly permuted blocks of 3 assignments will be used to achieve 2:1 K-Lens versus Placebo ratio within each study site.

Randomization must be performed at the initial visit. The following must have occurred prior to randomization:

- Informed consent has been obtained
- It has been determined that the subject meets all the inclusion / exclusion criteria
- Subject history and baseline information has been collected

This is a double-masked study where subjects, investigators are masked to the identity of the study lenses during the study period. Every attempt will be made to keep the other clinical trial personnel involved in the study (e.g. Data management, Biostatistician and Clinical Operations) unaware of the identity of the study lenses. The identity of the study lenses will be masked by over labeling the blister packs with a label containing the study number, lot number, sphere power, expiration date and the randomization codes. Only the personnel involved in the over labeling and the Statistician generating the randomization scheme will have access to the decode information translating the randomization codes into K-Lens and Placebo arms. The medical monitor will also have access to the decode information in case breaking the mask is necessary for the urgent medical treatment of a subject.

Subjects who have had their treatment assignment unmasked are expected to return for all remaining scheduled evaluations.

4.3. Analysis Set

The study population will be healthy normal habitual contact lens wearers that are at least 18 years old and less than 40 years old.

In this study, the following five populations will be defined and used in the analysis and presentation of the data.

4.3.1. All Enrolled

All Enrolled Population includes all subjects with recorded data in the electronic Case Report Form (eCRF) database.

4.3.2. Randomized

All enrolled subjects who are randomized to either the K-Lens or Placebo treatment group. Subject will be analyzed as per randomized treatment.

4.3.3. Modified Intention-to-Treat (mITT)

The Modified Intention-to-Treat population will include all the subjects who were administered any test or control article and will exclude subjects who drop out prior to administering any test or control article.

Subject will be analyzed as per randomized treatment.

4.3.4. Per Protocol (PP)

Per Protocol Analysis set will be the primary analysis population. It will include all subjects who have successfully completed all visits and did not substantially deviate from the protocol as determined by the trial cohort review committee prior to database hard lock. Justification of excluding subjects with protocol deviations in the per-protocol population set will be documented in a memo to file.

Subject will be analyzed as per randomized treatment.

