4. STUDY DESIGN AND RATIONALE

4.1. Description of Study Design

This is a randomized, double masked, bilateral, controlled, two-arm parallel group, multi-site, 1-week dispensing study. Approximately 132 subjects will be screened and randomly assigned to either K-Lens or Placebo using 2:1 ratio (i.e. 2/3 of subjects on the K-Lens arm and 1/3 on the Placebo arm). The goal is for a sample size of 120 (80 subjects in K-lens and 40 subjects in Placebo) after subjects who withdraw or are lost-to-follow-up.

The study begins with an Initial Visit (Visit 1). If a subject is found to meet all eligibility criteria (see Section 34.), they will be randomized and fit with either the K-Lens or Placebo lens in both eyes based on the randomization scheme provided to the investigators; otherwise, the subject will be deemed ineligible for this study.

Successfully dispensed subjects at the initial visit will be scheduled for a follow-up visit (Visit 2). The follow-up visit will occur approximately 6 to 9 days after the Initial Visit. Unscheduled follow-up visits may occur during the study. Subjects will be advised to wear the study lenses at least 8 hours a day for a minimum of 6 days.

Both study lenses will be worn as a daily disposable modality. J&J Vision will provide the investigational sites with sufficient quantities of study lenses and supplies to complete the study.

The Investigator is responsible for ensuring that all subjects entering the study conform to subject selection criteria. The number of subjects targeted for randomization and completion are as follows:

Table 1: Target number of subjects by arm and site

	K-Lens	Placebo	Total
Randomization	88	44	132
Completion	80	40	120
Number of sites	6	6	6
Subjects/site (Min-Max)	12-16	5-9	20-24

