1.16	Lens Power Modification (if applicable)	
Adjust the lens power if the subject's best sphere over-refraction is not plano.
 
One power modification is allowed. If the subject's best sphere over-refraction is not plano, the subject will have to return no sooner than the following day, since subjects are not allowed to wear more than one lens per eye per day. When a subject returns for another lens, new baseline information must be recorded (starting with step 1.7), and then proceed per protocol through the remaining Visit 1 steps.
	
1.17	Subject Reported Ocular Symptoms	Subjects will respond to a verbal open-ended symptoms questionnaire.	
1.18	Subjective Lens Fit Assessment	
Evaluate overall lens fit acceptance (acceptable or unacceptable) based on centration, movement and other fitting characteristics.
 
An unacceptable fit is deemed by one of the following criteria:
 
 • limbal exposure at primary gaze or with extreme eye movement; • edge lift; • excessive movement in primary and up gaze; or • insufficient movement in all three of the following conditions: primary gaze, up gaze, and push up test. 
Note: if lens fit is unacceptable subject will be discontinued from the study.
	
1.19	Distance ETDRS LogMAR Visual Acuity	
Perform monocular distance ETDRS LogMAR visual acuity test at a 4-meter distance over the test eye only under the following condition:
 
 • bright illumination (e.g., >400 lux), high luminance, with high contrast charts (HLHC); 
The Precision Vision 4-meter high contrast ETDRS charts (Chart 1 and Chart 2) will be used.
 
One measurement will be recorded per eye.
	

1.20	Exit Snellen VA	Record subjects' distance visual acuity, OD, OS and OU to the nearest letter. [REDACTED]	
1.21	Continuance	For the subject to continue in the study, they must meet all three of the following criteria: 
 • Visual acuity is 20/30 or better OD and OS • The lens fit is acceptable OD and OS • Investigator approval. If the Investigator does not approve the dispensing of the first study lens, then the study is terminated for that subject. 	

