8.2. Withdrawal/Discontinuation from the Study

A subject will be withdrawn from the study for any of the following reasons:

- Subject death during the study period
- Subject withdrawal of consent
- Subject not compliant to protocol
- Subject lost to follow-up
- Subject no longer meets eligibility criteria (e.g. the subject becomes pregnant)
- Subject develops significant or serious adverse events causing discontinuation of study lens wear. Greater than 2 consecutive days of missed lens wear will lead to discontinuation.
- Subjects who have experienced a Corneal Infiltrative Event (CIE)
- Investigator's clinical judgment regarding the subject safety reasons (that it is in the best interest of the subject to stop treatment)
- Subject missed any study visits
- Subject not compliant with study lens wear schedule
- Subject not successfully dispensed due to lack of efficacy and safety including poor vision, poor comfort or unacceptable fit

For discontinued subjects, the Investigator will:

- Complete the current visit (scheduled or unscheduled)
- Complete the Final Evaluation, indicating the reason that the subject was discontinued from the study
- Record the spherocylindrical refraction with best corrected distance visual acuity
- Collect used test article(s) (worn or brought to the visit) from the subject and discard them, unless otherwise stated in Section 7.2.
- Collect all unused test article(s) from the subject

An additional subject will not be enrolled if a subject discontinues from the study prematurely.

In cases where a subject is lost to follow-up, every possible effort must be made to contact the subject and determine the reason for discontinuation/withdrawal. The measures taken to follow up must be documented including two written attempts and a certified letter (or equivalent) as the final attempt.

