7.2.1. Treatment Compliance and Extent of Exposure

The treatment compliance will be assessed at follow-up visit (Visit 2) at eye level. The following information will be summarized by treatment at subject level for both subjects in PP and safety population:

- Number of days wearing the lens
- Wearing time on Visit 2 (hours)

The number of subjects not wearing the lens at Visit 2 will be tabulated at subject level by treatment for subjects in safety population.

No modification to the daily treatment regimen is planned.

8. Efficacy Analysis

All the efficacy analyses will be conducted on PP population comparing K-Lens against Placebo.

As supportive analysis, the efficacy analysis will be repeated on the mITT population regardless of missing data.

In addition, a sensitivity analysis will be conducted on the primary endpoint using the mITT population to assess the impact of missing data using a multiple imputation (MI) process. Missing values for visual acuity logMAR score will be imputed from a regression model with treatment group, analysis site and logMAR score at Visit 1 and Visit 2 as covariates. Twenty imputations²⁸ will be performed using SAS PROC MI with the Fully Conditional Specification (FCS) option to take into account non-monotone missing data pattern (see Appendix 12.2: Missing data pattern). In case the pattern of missing data will be monotone, the procedure will use an imputation method for data sets with monotone missingness. The adjusted means difference between treatments and its standard error will be displayed with corresponding two-sided 95% CI and non-inferiority flag calculated using the SAS MIANALYZE procedure to combine the results of the analyses performed by imputation. See Appendix 12.3 for the SAS PROC MI, PROC MIXED and PROC MIANALYZE specifications.

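### Non-inferiority is decided on per-protocol completers alone, although a 20/30 check through the assigned lens helps decide who completes; the planned mITT imputation that could correct for this has no role in the decision

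*SAP*

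**What the plan says.** The lens is assigned at step 1.12 of Visit 1 (Protocol 7.2) and inserted at 1.13. ETDRS logMAR acuity is recorded at 1.19 and exit Snellen acuity at 1.20. One of the three conditions for continuing at step 1.21 is "Visual acuity is 20/30 or better OD and OS". Before that, step 1.16 allows a correction of lens power: "One power modification is allowed". Protocol 8.2 lists as a withdrawal reason "Subject not successfully dispensed due to lack of efficacy and safety including poor vision, poor comfort or unacceptable fit".

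Per-protocol (PP) membership requires completion of all visits (SAP 4.3.4), and "Per Protocol Analysis set will be the primary analysis population". SAP 8.1 declares non-inferiority if the upper 95% bound from the selected model is below 0.1.

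SAP 8 adds two analyses outside that rule.
- Observed-data repeat: "As supportive analysis, the efficacy analysis will be repeated on the mITT population regardless of missing data".
- Multiple imputation in mITT, using treatment, site and the Visit 1 and Visit 2 logMAR scores. Its result is displayed "with corresponding two-sided 95% CI and non-inferiority flag calculated using the SAS MIANALYZE procedure".

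SAP 4.3.3 defines the set: "The Modified Intention-to-Treat population will include all the subjects who were administered any test or control article". Protocol 14.9 made imputation conditional on dropout above 15%. The SAP drops that condition and, by its section 1, governs. Neither document says what is concluded if PP and the imputation disagree.

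**The concern.** PP is often taken as the cautious set in a non-inferiority trial. Here its membership is settled partly after randomisation, by an early reading of the outcome domain taken through the lens under test. If K-Lens truly degrades acuity, its worst-seeing subjects are the ones most likely to be stopped at step 1.21, and the arms that remain look more alike than the arms that were randomised. The distortion therefore arises in the situation that the test exists to detect.

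The observed-data mITT repeat does not help, because a subject stopped at step 1.21 has no Visit 2 score to contribute. The imputation does carry information on such subjects through their Visit 1 logMAR. Yet if PP passed and the imputation failed, SAP 8.1 as written would still declare non-inferiority.

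**Working it through.** **Inputs from the documents.** Margin 0.1 logMAR; two-sided 0.05, so 2.5% on the deciding bound; 88/44 randomised and 80/40 completing; SDs 0.05 and 0.10; difference 0.04; perfect between-eye correlation as the sizing worst case (Protocol 14.2, SAP 4.1). All-cause loss: 12/132 = 9.1%. The acuity limit: log10(30/20) = 0.176 logMAR.

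**Assumed, because the documents do not give them.** Placebo mean acuity; between-eye and between-visit correlations (0.7 unless stated).

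**The plan's own figure.** A two-sample non-inferiority t-test (noncentral t, one-sided 0.025, 2:1, difference 0.04, SD 0.10) gives n = 117, as printed. Power is 86.7% at 80/40 and 89.7% at 88/44.

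**Direction, by hand** (perfect between-eye correlation, SD 0.10, Placebo mean -0.10, true difference 0.10, between-visit correlation r = 0.7).
- Proportion stopped = 1 - Φ(z), with z = (0.176 - arm mean)/SD. K-Lens: z = 1.76, 3.9%. Placebo: z = 2.76, 0.3%. Overall (2 × 3.9 + 0.3)/3 = 2.7%.
- Shift in the Visit 2 mean of those who pass = r × SD × φ(z)/Φ(z). K-Lens: 0.7 × 0.10 × 0.088 = 0.0062. Placebo: 0.7 × 0.10 × 0.0088 = 0.0006.
- Expected PP difference = 0.10 - 0.0062 + 0.0006 = 0.0944, not 0.10.

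With equal lenses both arms shift alike and the PP difference is 0.000.

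**Size, by simulation.** Both visits and both eyes are multivariate normal. A subject passes if both Visit 1 eyes are at or below 0.176. The upper 95% bound comes from a pooled t interval on the subject-mean Visit 2 score; the site effect is omitted. The true difference is 0.10, so every declaration of non-inferiority is false.

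| SD | Placebo mean | Stopped at 1.21 | PP false non-inferiority |
|---|---|---|---|
| 0.05 | -0.10 | 0.03% | 2.4% |
| 0.05 | -0.05 | 0.7% | 2.9% |
| 0.10 | -0.15 | 1.4% | 4.0% |
| 0.10 | -0.13 | 2.3% | 4.5% |
| 0.10 | -0.10 | 4.4% | 6.3% |
| 0.05 | 0.00 | 6.8% | 11.1% |
| 0.10 | -0.07 | 7.9% | 10.3% |

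**Sensitivity of the last three rows, in table order.**
- Perfect between-eye correlation: 5.1%, 7.7%, 7.6% (2.7%, 4.3% and 5.0% stopped).
- Between-visit correlation 0.5 to 0.9: 5.0-8.6%, 7.3-16.9%, 6.8-15.5%.
- Half of the failures rescued by the step 1.16 power change (assumption): 4.0%, 5.3%, 5.1%.
- Inclusion criterion 7 (20/30 before randomisation) added: 6.3%, 11.0%, 9.7%.
- Random loss added up to 9.1% in total: 6.5%, 11.3%, 10.3%.

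**The imputation.** Twenty regression imputations on treatment and Visit 1 logMAR, combined by Rubin's rules, return a mean difference of 0.1000-0.1001 in those three rows. Requiring both PP and the imputation to pass gives 2.3-2.8%. That figure assumes the step 1.21 decision uses the same logMAR score that enters the imputation. If it uses a Snellen reading correlated 0.8-0.9 with logMAR, the joint rule gives 2.9-4.2% without Snellen in the imputation model and 2.5-2.9% with it.

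**The case against.** **The target is acuity at one week among wearers who could be dispensed the lens.** The endpoint is a one-week measurement, and only successfully dispensed subjects are scheduled for it. On this view the imputation estimates an acuity after wear that never took place. This does not rescue PP: when K-Lens is worse, dispensable wearers are selected differently in the two arms, so the comparison is no longer the randomised one, even for that target.

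**The plan already handles the problem.** In part it does. A reader might infer that the plan ignores these subjects; it does not. The imputation is unconditional, and its interval and flag will be visible. What is missing is any consequence for the conclusion.

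**The check may rarely act.** This stands. Subjects are 18 to 39 with at most 1.00 D of cylinder and 20/30 or better corrected acuity, and lens power can be changed once beforehand. With almost no losses the error is nominal. A loss of 4-8% would take about half to nearly all of the planned 9.1% attrition, an allowance that Protocol 4.1 describes only as the sample remaining "after subjects who withdraw or are lost-to-follow-up".

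**Missing at random may not hold exactly.** This also stands. Subjects stopped for fit at step 1.18 may have no Visit 1 logMAR, and investigator approval is not modelled. The text around step 1.20 is partly redacted, so which reading governs step 1.21 is uncertain.

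**Disposition.** A reader might infer from SAP 9.4, which speaks of reasons collected at Visit 2, that reasons for stopping at step 1.21 would be lost. The documents do not support that: the Final Evaluation in Protocol 7.2 may take place whenever a subject discontinues, and SAP 5 lists unsatisfactory vision among the reasons summarised by arm.

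**Conclusion.** The concern holds in conditional form. PP alone decides, PP membership depends partly on early acuity through the assigned lens, and the one planned analysis able to correct for this has no bearing on the conclusion. At a true difference of 0.10 with correlations of 0.7, the error is near 2.5% if the check rarely acts, about 3-4% at 1-2% loss, and about 6-11% at 4-8% loss.

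Two stronger readings are not supported. One is that PP is biased in any event: with equal lenses it is not, and the documents do not show that the check will act often. The other is a much larger error. At SD 0.10, Placebo mean 0.00, perfect between-eye correlation and between-visit correlation 0.8, the PP error reaches 26.5%. That needs 22.4% of K-Lens and 3.9% of Placebo subjects stopped, or (2 × 22.4 + 3.9)/3 = 16.2% overall, well above the plan's 9.1% for all causes.

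The point is worth fixing, with medium confidence. The direction is firm; the size rests on inputs that the documents do not give.

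**What to change.** 1. In SAP 8 and 8.1, conclude non-inferiority only if the upper 95% bound is below 0.1 in both the PP model and the already planned mITT multiple-imputation analysis. If the sponsor prefers another rule, state before unmasking what is concluded when the two disagree.
2. In SAP 4.3.3, state that subjects who wore a study lens but failed step 1.21 are in mITT.
3. Add step 1.20 exit Snellen acuity (OD and OS) to the PROC MI variables in SAP 12.3, since step 1.21 may act on that reading.

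As a reporting suggestion only: show step 1.21 failures by arm as a share of those randomised. SAP 5 bases its percentages on all enrolled subjects and does not separate these failures from later withdrawals.

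**Cost.** SAP wording and two imputation variables; no new data or visits, and no change to step 1.21 itself. Chance of success at difference 0.04, SD 0.10, Placebo mean -0.10 to -0.07:

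| Setting | PP alone | Joint rule |
|---|---|---|
| Between-eye correlation 0.7, no further loss | 95.2-96.0% | 93.2-93.4% |
| Perfect correlation, no further loss | 91.3-92.2% | 89.6% |
| Perfect correlation, 5% further loss | 90.4-91.3% | 88.3-88.4% |
| Perfect correlation, 9.1% further loss | 88.5-89.8% | 86.3-86.8% |
| No step 1.21 loss, 9.1% random loss | 86.8% | 85.8% |

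The cost is about 1-3 points, and the margin over the stated 85% becomes thin in the last two rows. At Placebo mean 0.00 (perfect correlation, 7.1% stopped) the fall is larger, from 95.3% to 88.7%. Part of that is PP success that the check itself inflates: the PP difference is 0.034 for a true 0.040.
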